4.3.4 Effectiveness Hypotheses (at 30-day follow-up assessment)

Patients in the IF evaluation period compared with baseline evaluation period will:

1. Report fewer days with illicit opioid use in the past 7 days
2. Experience fewer overdose events (past 30 days)
3. Report fewer HIV risk taking behaviors (past 30 days)
4. Utilize fewer inpatient OUD services (past 30 days)
5. Have greater rates of illicit opioid negative urine tests at 30 days

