10.2.8 Timeline Follow-back (TLFB)

The Timeline Follow-back procedure (Sobell & Sobell, 1992²⁸; Fals-Stewart, 2000³⁴) will be used to elicit the patient participant's self-reported use, quantity, and route of administration of opioids, marijuana, stimulants, benzodiazepines and alcohol. At enrollment, substance use is reported by the patient participant for the 7-day period prior to informed consent.²⁸ At the 30 day follow-up visit, substance use is reported for the 7 days prior to study day 30.

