10.2.15 Engagement in Treatment Survey

At 30 days post enrollment, participants will be asked to report OUD treatment received on their 30th day post enrollment target date (Day 30, with the ED enrollment visit being Day 0). Data will be reported on the Engagement in Treatment: Patient Survey. The effectiveness outcome will be confirmed with the addiction treatment provider. Engagement is based on enrollment in treatment on the 30th day post enrollment (Enrollment is considered Day 0). The Engagement in Treatment: Facility survey includes the type of treatment the participant is receiving, i.e., methadone, buprenorphine and/or naltrexone treatment, detoxification, residential or inpatient treatment. Date of admission is recorded as well as the level of treatment received according to ASAM Levels of care, such as Level I: Outpatient Treatment; Level II: Intensive outpatient treatment (including partial hospitalization); Level III: Residential/Inpatient Treatment; Level IV: Medically managed intensive inpatient treatment or Other-specified.

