11.8 Administration of BUP During IF Evaluation Period

The following procedures will be incorporated into the training of ED providers during the IF period. We will assess fidelity to the procedures (adherence) using a critical action checklist. The checklist will include confirmation of documentation of: urine toxicology and liver function tests obtained; patient participant meets criteria for DSM-5 moderate-severe opioid use disorder; urine positive for opioid; formal assessment of Clinical Opioid Withdrawal Scale (COWS); ED-initiated BUP provided; BUP education and induction instructions provided; and referral for ongoing medication assisted treatment. Education regarding BUP and Induction is provided; and Appointment for ongoing MAT provided. Providers will be instructed to induce patients onto BUP using an induction and stabilization protocol that has been well tolerated by patients in our previous study.⁷ Buprenorphine induction will take place in the ED or unobserved, and should be based on the study patient's level of opioid withdrawal as measured by the COWS. Depending on the study patient's level of physical dependence, the goal of the induction will be 8mg on the first day and 16mg on subsequent days. Study patients will receive a dose in the ED if they exhibit moderate to severe withdrawal on the COWS and will leave with a prescription for the daily doses needed prior to their scheduled follow-up appointment, and their significant others, will be provided with instructions for unobserved induction if their COWS score indicates less than mild withdrawal (Mild 5-12) at the time of the ED visit. Unobserved induction has become common practice⁵⁰ and was used successfully in our prior study of ED-initiated BUP. Unobserved induction will also have a goal of 8mg on the first day. In an effort to maximize retention and abstinence achievement during the induction we will instruct ED providers to provide study patients with a scheduled appointment for follow up with an office-based BUP provider or an OTP within 96 hours of their ED visit.

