12.5 Hypothesized Treatment Effect Sizes

We anticipate that during the baseline evaluation period, the rates of ED-initiated BUP treatment for OUD (primary implementation outcome) will be very low at each of the study sites (less than 15% of all eligible patients). Based on our prior work and other published research, we estimate that the rates of participation in a formal addiction treatment on the 30th day post enrollment (effectiveness outcome) will be approximately 25% for patients with OUD enrolled in the baseline evaluation period.

We anticipate that during the IF evaluation period, at each of the study sites, at least 25% of all eligible patients with OUD will receive ED-initiated BUP with referral for ongoing MAT. Based on our prior research, we also anticipate that approximately 40-50% of patients with OUD enrolled during the IF evaluation period will be engaged in formal addiction treatments at 30 days. The expected treatment effects of this section are summarized in Table 3 below.

12.5.1 **Table 3:** Hypothesized Probabilities of Success

Outcome	Baseline Evaluation Period	IF Evaluation Period
Implementation	< 15%	25%
Effectiveness	25%	40-50%

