7.6.2 Secondary Effectiveness Outcomes

1. Self-reported days of illicit opioid use (past seven-days) as measured by TLFB method at 30 days: The following substances collected on TLFB method will be considered illicit opioid use if there is no prescription: heroin, oxycodone, hydrocodone, fentanyl, morphine, hydromorphone, meperidine, methadone, buprenorphine, oxymorphone, pentazocine, and codeine.
2. Overdose events (past 30 days) captured by participant self-report in ODE: The outcome will be scored from question 1 “On how many days in the past 30 days do you think you overdosed on opioids (you used more opioids than you should have used and were more sedated, drugged, or high than you wanted to be)?”
3. HIV risk taking behaviors (past 30 days) as captured in HST.
4. Healthcare service utilization (past 30 days).
5. Rates of illicit opioid negative urines at 30 days as captured on urine drug screen (UDS): A UDS will be considered negative for opioids if all of the following substances are negative: opiates (2000ng), oxycodone, methadone, opiates (300ng), buprenorphine and fentanyl. If a participant tests positive on the UDS for any of these substances and self-reports on TLFB that they have a prescription for any opioid, then the use will be considered licit (i.e., not illicit).

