9.0 SIGNIFICANCE TESTING AND MULTIPLICITY

As this study is designed as a Hybrid Type 3 Effectiveness-Implementation study, the implementation is the main outcome, and so when measuring success of the study, the implementation outcome will take precedence over the effectiveness outcome, which will be considered secondary. Therefore, considering the effectiveness aim as secondary, it is not necessary to put in procedures to control the type 1 error across multiple outcomes. Multiple-comparison adjustments are not anticipated when performing secondary analyses. To be mindful of the multiple testing problem, secondary findings will be reported as noteworthy hypothesis-generating results only when their p-values are considerably smaller than 0.05.

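### The day-30 urine outcome excuses any opioid-positive sample, fentanyl included, if the patient reports a prescription for any opioid, so more prescribing would look like less illicit use

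*SAP*

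**What the plan says.** Protocol 4.3.4 predicts that IF-period patients will "Have greater rates of illicit opioid negative urine tests at 30 days", but the protocol never defines an illicit positive. The definition is in SAP 7.6.2 item 5. A sample is negative if all six assays are negative: opiates at two cut-offs, oxycodone, methadone, buprenorphine and fentanyl. If any is positive and the patient "self-reports on TLFB that they have a prescription for any opioid, then the use will be considered licit (i.e., not illicit". Nothing links the prescription to the assay that was positive.

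Item 1 of the same section covers self-reported days of use. Its listed substances "will be considered illicit opioid use if there is no prescription: heroin, oxycodone, hydrocodone, fentanyl" and others. It does not say whether the prescription must be for that substance.

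Two protocol passages fix the timing. In 10.2.8: "At the 30 day follow-up visit, substance use is reported for the 7 days prior to study day 30". In 11.8, patients dosed in the ED "will leave with a prescription for the daily doses needed prior to their scheduled follow-up appointment".

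On expected effects, Protocol 12.5 puts day-30 engagement at about 25% in the baseline period and anticipates that "approximately 40-50% of patients with OUD enrolled during the IF evaluation period will be engaged in formal addiction treatments at 30 days". SAP 9.0 states that "secondary findings will be reported as noteworthy hypothesis-generating results only when their p-values are considerably smaller than 0.05".

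**The concern.** Some exemption is needed, because otherwise a patient taking buprenorphine as prescribed would count as using illicitly. The fault is its breadth. A patient prescribed buprenorphine whose urine is positive for fentanyl is scored the same as one whose urine shows buprenorphine alone.

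The ED prescription only bridges to the follow-up appointment, and the follow-up TLFB looks at the 7 days before day 30. The exemption therefore rests mainly on continued, mostly community, prescribing around day 30. The intervention aims to start buprenorphine and link patients to ongoing medication treatment, so that prescribing may well differ between periods. If it does, the outcome partly re-measures receipt of treatment while being reported as drug use. A reader could not tell fewer unprescribed opioids from more prescriptions. No planned sensitivity analysis addresses this; those in SAP 7.5.2 concern the COVID-19 pause and the two primary outcomes.

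**Working it through.** The documents give no expected rate or power for this outcome, so there is no planned figure to reproduce. The check applies the scoring rule algebraically to patients with a urine result.

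**Notation**
- q0, q1: share reporting any opioid prescription, baseline and IF periods
- h: share of those patients with an unprescribed positive
- m: share illicit-negative among patients without a prescription

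That a sample called licit is counted as illicit-negative is inferred from the outcome's name; it is the natural reading.

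**Formulas, per period**
- SAP rule: q + (1 - q)m
- Matching drug to assay: q(1 - h) + (1 - q)m
- Overstatement: q × h

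With h equal in both periods, the between-period artefact is (q1 - q0) × h. With m also equal, the SAP rule reports a difference of (q1 - q0)(1 - m). This does not contain h: the reported gain is the same whether all of the prescribed patients stopped unprescribed use or none did.

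**Assumed ranges.** q0 10-20%, q1 25-40%, h 30-70%.
- Smallest: (0.25 - 0.20) × 0.3 = 0.015, or 1.5 points
- Largest: (0.40 - 0.10) × 0.7 = 0.21, or 21 points
- Midpoints (q0 = 0.15, q1 = 0.325, h = 0.5, m = 0.5):
  - SAP rule: 0.15 + 0.85 × 0.5 = 0.575 and 0.325 + 0.675 × 0.5 = 0.6625, a gain of 8.75 points
  - Matched: 0.15 × 0.5 + 0.85 × 0.5 = 0.50 and 0.325 × 0.5 + 0.675 × 0.5 = 0.50, a gain of 0

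**Using the plan's engagement rates (25% to 40-50%).** Assume 50-100% of engaged patients, and no others, report a prescription.
- Smallest: 0.15 × 0.5 × 0.3 = 0.0225, or 2.3 points
- Largest: 0.25 × 1.0 × 0.7 = 0.175, or 17.5 points

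**Chance of a false positive finding.** Protocol 12.14.4 analyses this outcome with the 12.14.1 model, one-sided at 0.05. The table uses a plain two-proportion test at that level, with unprescribed positivity the same in everyone (h = 1 - m) and unchanged between periods. Planned enrolment is 4 × 120 = 480 per period; 336 assumes that 70% give urine. Site clustering and the time term are ignored, so the probabilities are only a guide.

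| Prescription share | h | Scored negative | False gain (points) | Rejection, n = 480 | Rejection, n = 336 |
|---|---|---|---|---|---|
| 12.5% to 20% | 0.3 | 73.75% to 76.0% | 2.25 | 0.200 | 0.165 |
| 12.5% to 25% | 0.7 | 38.75% to 47.5% | 8.75 | 0.864 | 0.741 |
| 25% to 40% | 0.3 | 77.5% to 82.0% | 4.5 | 0.536 | 0.423 |
| 25% to 40% | 0.5 | 62.5% to 70.0% | 7.5 | 0.792 | 0.660 |
| 25% to 40% | 0.7 | 47.5% to 58.0% | 10.5 | 0.948 | 0.862 |
| 25% to 50% | 0.7 | 47.5% to 65.0% | 17.5 | 1.000 | 0.999 |

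With matching, the difference is 0 in every row and the rejection rate is 0.05.

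**If treatment does reduce use.** Suppose prescribed patients are half as often positive: h = 0.25 against 0.5 in the others, with the share rising from 25% to 40%. The true gain is 0.15 × (0.5 - 0.25) = 3.75 points. The rule reports 0.15 × 0.5 = 7.5, twice the truth.

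**The case against.** The strongest objection is to the size. Neither q nor h comes from the documents. The 21-point figure combines the far corners of assumed ranges. The midpoint case gives prescribed patients the same rate of unprescribed use as everyone else, although the protocol's background reports less illicit use with ED-initiated buprenorphine. This stands as a caution on magnitude: if h were zero the artefact would vanish. With h at half the rate of other patients, though, the reported gain is still double the true one.

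The engagement-based range also mixes denominators. Engagement rates are planned over all enrolled patients with losses counted as failures (Protocol 12.10), whereas urine exists only for patients seen in person (Protocol 9.4). Engaged patients need not be on medication (SAP 7.3). That range illustrates the scale; it does not confirm the other one.

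Item 1 lists substances one by one, so it can be read substance by substance. On that reading it would be a sounder companion outcome. The text does not settle the reading.

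The follow-up visit can fall after day 30 (SAP 3.3.2), while the TLFB stops at day 30. Urine and prescription report may therefore refer to different dates. This is true, but it affects the present rule and a matched rule alike.

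Finally, this is one of five secondary effectiveness outcomes. That limits the consequence but does not make the rule right.

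**Conclusion.** The concern holds. As written, item 5 classes unprescribed fentanyl or opiate use as not illicit in any patient reporting an opioid prescription, and nothing else in the protocol or SAP corrects this. The misclassification follows from the text alone. The between-period bias also requires day-30 prescribing to differ between periods, which the trial's aims make plausible but the documents do not quantify.

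Under the stated assumptions the artefact is 1.5 to 21 percentage points, and 2.3 to 17.5 when tied to the planned engagement rates. It favours whichever period has more day-30 prescribing. The Revised SAP section reports that engagement fell at one site, and there the artefact could run the other way. Both primary outcomes are untouched. The rule should be corrected before this outcome is used to describe illicit opioid use.

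**What to change.** Rewrite item 5 so that a positive assay is licit only if the TLFB reports a prescription for a drug that explains that assay. Any other positive makes the sample illicit-positive. State the map before re-scoring:

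- buprenorphine, methadone, oxycodone and fentanyl: each to its own assay
- prescribed opiates such as morphine or codeine: to the opiates assays
- item 1 drugs without an assay of their own (hydrocodone, hydromorphone, oxymorphone, meperidine, pentazocine): as given in the test-kit documentation

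In item 1, specify no prescription for that substance. Report positives by assay and period beside the derived outcome. If the urine data have already been analysed, label the re-scoring post hoc.

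The cost is one derivation rule, one mapping table and one wording change. Assay results are already collected. Item 1 implies that prescription status is held by substance, but the Table 11 shell splits it only for opioid analgesics, so confirm that it exists for buprenorphine and methadone. If it does not, Protocol 10.2.15 offers a fallback: "The Engagement in Treatment: Facility survey includes the type of treatment the participant is receiving, i.e., methadone, buprenorphine and/or naltrexone treatment". That form records treatment rather than prescriptions and may be missing for some patients. Observed illicit-negative rates will be lower under the matched rule.

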7.7 Exploratory Analyses

We will also evaluate a limited set of patient and provider characteristics for their potential effect on successful implementation and effectiveness outcomes. Study participant characteristics to be evaluated are:

- Gender
- Race/Ethnicity
- Health insurance status
- Age
- Primary drug (heroin vs prescription opioids)
- Reason for presentation such as seeking treatment for OUD or overdose

- Referral to office-based BUP provider versus OTP
- Pain Intensity and Interference (PEG scale)
- Opioid overdose at index visit
- Stimulant positive urine toxicology, or self-report at index ED visit
- Fentanyl positive urine toxicology at index ED visit

ED characteristics such as size, location, existing substance abuse services and follow up resources as well as the range and number of addiction treatment services in the catchment area of the ED will be described, as well as ED provider characteristics such as age, gender, years, and level of training will be evaluated.

These analyses will utilize similar models as for the primary analysis, the MIXED models procedure repeated measures and generalized estimating equations (GEE), or other appropriate regression, clustering, and factor analytical tools to evaluate potential impact of site factors and patient characteristics on the primary implementation outcome and effectiveness outcome.

For cost effectiveness analyses, resource costs will include intervention costs incurred in the ED related to the studied intervention, (e.g., cost to provide ED-initiated BUP with referral for ongoing MAT, cost of buprenorphine), downstream medical costs and patient costs of treatment (e.g., time, transportation). Where relevant, we will convert duration of an activity to monetary values by multiplying by provider labor costs. The costs of all addiction and medical treatment (e.g., inpatient, outpatient, treatment center, medication) received by participants will be included in the cost calculations. This information will be collected by self-report through a health service utilization survey. Unit costs of substance abuse and medical treatment will come from the facility surveys or other published estimates.⁷ Medication costs will be calculated from the average wholesale price plus the dispensing fee. We will collect Medicare reimbursement rather than Medicaid or commercial insurance amounts for relevant services in the facility surveys because Medicare reimbursement is most likely to reflect marginal costs of service provision. Incremental cost effectiveness ratios will be calculated, defined as $\Delta C/\Delta E$, where ΔC is the difference in costs and ΔE is the difference in effectiveness between the baseline evaluation period and IF evaluation period. Effectiveness is narrowly defined to the primary outcome – engagement in formal addiction treatment for OUD. The drawback of incremental CEA is that because no outcome is comprehensive, analyses do not allow one to directly compare interventions with different outcome measures. Yet, policymakers may still value this information when choosing among competing programs. Researchers often use the outcome Quality Adjusted Life Years (QALYs) to enable comparisons across interventions. In the case of OUD, many of the benefits accrue to individuals other than the individual being treated and would not be captured in this metric making this outcome less appealing. Because health care costs are typically highly skewed, we will consider several cost estimation models. We will not include monetized values of societal outcomes (i.e., reduced criminal activity) because inclusion of these monetized values of these outcomes in the numerator of the cost effectiveness ratio would lead to double counting of these outcomes (e.g., their monetized value would be counted in the numerator and then counted again as the value of being abstinent in the denominator of the cost effectiveness ratios). We will not include training or research costs because these costs would not be incurred in standard care. Our primary outcome will be cost effectiveness acceptability curves, which indicate the probability different implementation strategies are cost effectiveness at different willingness to pay threshold values of the studied outcome. For cost estimates which are subject to debate either because of known imprecision in the estimation procedures or lack of adequate information, we will conduct sensitivity analyses with the goal of explaining the ways in which different assumptions would impact study results.

We will use appropriate non-parametric, parametric, and analysis of variance statistical procedures to descriptively evaluate the key characteristics of each study site (e.g., patient flow indicators such as length of stay of treated and released patients, and demographic and drug use characteristics of patients with OUD presenting at each ED site, indicators of organizational level differences between the sites (e.g., the number ED providers, number/ratio ED providers DEA waivered to prescribe BUP), and to evaluate comparability of baseline characteristics among patient cohorts enrolled at each of the study sites and overall during baseline evaluation period and the IF evaluation periods across all sites.

The EHR-abstracted data regarding MOUD activities in the ED will be summarized by site at the following time points separately: (1) the entire BEP; and (2) the entire IFEP. Exploratory analyses may evaluate whether any of the measures in this dataset are associated with primary implementation factors.

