4.4.2 Cost effectiveness

We will perform an incremental cost effectiveness analyses (CEA) and calculate the incremental cost per unit increase in engagement in formal addiction treatment comparing patients in the IF evaluation period with those in the baseline evaluation period.

We will perform incremental cost effectiveness analyses (CEA) to evaluate if effectiveness benefits are worth the additional costs.

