5.2 Implementation Facilitation Leads to Practice Change

IF is defined as a “process of ‘helping individuals and teams to understand what they need to change and how they need to change it in order to apply evidence to practice.’”¹⁸ IF is an effective intervention⁵ that includes a “deliberate process of interactive problem solving and support that occurs in the context of a recognized need for improvement and supportive interpersonal relationship.”¹⁷ A recent systematic review and meta-analysis found that IF has a positive impact on guideline adoption in primary care.⁵ A central aspect of IF includes the active role of the facilitator(s) working in partnership with relevant stakeholders, and other implementation intervention components.^{17,18} Importantly, IF involves a “formative evaluation” to identify the specific and dynamic needs of stakeholders and the context (i.e., ED) for implementation of evidence-based practices.¹⁸ This “diagnostic” formative evaluation informs the initial tailoring and refinement of the IF, which includes the “bundle” of services¹⁸ (Table 1) tailored to meet site-specific needs. The formative evaluation process is iterative and occurs during the 6 month IF period and continues throughout the IF evaluation period.¹⁹ Tailored implementation strategies have been found to be more effective than non-tailored interventions in changing practice²⁰ and have been applied to changing primary care and mental health treatment delivery.^{8,21} IF has been used by large healthcare organizations including the Veterans Health Administration and is endorsed by the Agency for Health Care Research and Quality as a way to assist practices in becoming Primary Care Medical Homes.²²

5.2.1 **Table 1:** Components of Implementation Facilitation

Component	Description
External Facilitator	Outside content expert who assists site
Local Champion	Local site stakeholder who promotes change
Provider Education and Academic Detailing	Provision of unbiased peer education
Stakeholder Engagement	Aligning goals of implementation and those impacted
Tailor Program to Site	Addressing site-specific needs based on formative assessment
Performance Monitoring and Feedback	Assess implementation of treatment efforts
	and inform site of results
Formative Evaluation	Quantitative and qualitative determination of impact
Establish a Learning Collaborative	Shared learning opportunities tailored to stakeholders

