This will involve regular assessment of individual clinician performance and providing information about that performance.⁸ We will work with ED directors and other members of the ED staff to identify the optimal outcomes to be tracked as well as how often and in what format feedback will be provided based on ED and provider-level data. Outcomes will include the rate of BUP prescribed for eligible patients and follow up information regarding the patient's enrollment in treatment as well as individual provider adherence to critical actions on a checklist for prescribing BUP. These continual improvement activities will be integrated into the department's continuous quality improvement and feedback initiatives, similar to other clinical quality and safety measures such as door to balloon times used for patients who present to the ED with acute coronary syndromes. Emergency providers are accustomed to receiving daily operating reports such as patient length of stay, door to doctor and time to decision making. It is part of their world, and this will be integrated into their processes. The external facilitators in collaboration with trained and qualified personnel will provide additional training or educational booster sessions for sites with low implementation and those requesting such services.

FORMATIVE EVALUATION

- a) **Implementation-focused formative evaluation** will occur during the implementation and focus on the discrepancies between the implementation plan and its operationalization. Examples of processes that will be examined include: 1) number and types of educational training sessions attended by staff, 2) number of staff who view the audit and feedback reports, and 3) number of champions that attend facilitation meetings.
- b) **Progress-focused formative evaluation** meetings, led by trained and qualified personnel, will monitor achievement of implementation goals and performance targets to identify blocked progress, allowing steps to be taken to optimize the intervention. These meetings will focus on barriers and strategies to address identified barriers. Non-attendance of site participants will be documented and outreach through individual facilitation meetings, calls or emails will be initiated to assess for stalled progress and offer assistance.

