14.8 Clinical Monitoring

14.8.1 Data collection and data completeness monitoring

The primary implementation outcomes at each study site will be based on ED provider documentation of ED-initiated BUP with referral for ongoing MAT in the EHR. Medical records will be accessed by an RA blinded from the index visit. The data will be entered into Advantage eClinical and accessed at each site by the RA.

The effectiveness data will be obtained by study RAs at each site by conducting the 30-day follow up assessment. All study patient participant-reported treatment engagement information will then be verified directly with the provider/program. Loss of follow up will be mitigated by having the RA schedule a 30-day post enrollment follow-up appointment prior to ED discharge and provide a printed appointment card.

At baseline we will collect information on provider wages and space costs to perform interventions to use in cost analysis. Unit process for other health care treatments will come from published national data.

Data completeness will be monitored weekly by review of aggregates/summaries of data completeness reports. The DSC will produce completeness summaries for DSMB meetings and for Trial Progress Reports, which are posted daily on the internet for perusal by study leadership.

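### The cost-effectiveness analysis of Implementation Facilitation leaves out training, which is part of the intervention, so its incremental cost is set too low

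*SAP*

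**What the plan says.** The cost-effectiveness paragraph is the same in SAP 7.7 and protocol 12.15, so the rule is not a slip in one document. It makes four statements that matter here.

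- **Contrast.** The ratio is ΔC/ΔE, "where ΔC is the difference in costs and ΔE is the difference in effectiveness between the baseline evaluation period and IF evaluation period". Protocol 4.4.2 gives the same aim: to "calculate the incremental cost per unit increase in engagement in formal addiction treatment comparing patients in the IF evaluation period" with those in the baseline period.
- **Main output.** The principal result is a set of acceptability curves, "which indicate the probability different implementation strategies are cost effectiveness" at a range of willingness-to-pay thresholds.
- **Costs counted.** The "resource costs will include intervention costs incurred in the ED related to the studied intervention". The examples are the provision of ED-initiated buprenorphine with referral and the drug itself. Downstream medical costs and patient costs are added.
- **Costs not counted.** "We will not include training or research costs because these costs would not be incurred in standard care".

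Elsewhere, training is described as part of IF. Protocol Table 1 (5.2.1) lists provider education and academic detailing as a component, described as "Provision of unbiased peer education". Protocol 11.10 offers educational sessions and buprenorphine training to the providers involved, has the external facilitators train and coach, and supports completion of the DATA 2000 waiver. The comparator, in protocol 11.1, is one grand-rounds style lecture, traditionally 50 minutes long.

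**The concern.** An incremental analysis counts whatever differs between the two options. IF is what differs between the two periods, and training is one of its listed parts. The reason given for leaving training out is that standard care does not incur it. That is what makes it incremental. The reason works for research costs, which an adopting hospital would not bear. It does not work for training that the hospital would have to fund in order to obtain the effect in the denominator.

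The consequence is a mismatch: ΔE carries the full effect of IF, while ΔC carries only part of its cost. SAP 7.7 says that policymakers may use this result to choose among competing programs. Protocol 3.4 presents IF as a reproducible model for them. A reader deciding whether to adopt IF would see a ratio and curves that are too favourable.

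**Working it through.** The plan states no ICER and no training cost, so there is no figure to reproduce. The direction can be derived, and the size can be given per unit of omitted cost.

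**Inputs**
- Sites: 4; about 120 patients per site in each period (protocol 12.3). IF-period patients: n = 4 × 120 = 480.
- Planned engagement: 25% at baseline and 40–50% under IF (protocol 12.5, Table 3). ΔE = 0.15 to 0.25.
- ED providers engaged in IF: 25–30 per site (protocol 12.3), so 100 to 120 in all.
- T: total incremental training cost of IF, net of the grand-rounds session. It is not in the documents and is treated as an assumption.

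**Effect on the ICER**
- As planned: ΔC/ΔE. With training: (ΔC + T/n)/ΔE.
- Amount by which the planned ratio falls short: T/(n × ΔE).
- Extra engaged patients, n × ΔE: 480 × 0.15 = 72; 480 × 0.25 = 120.
- For T = $100,000: 100,000/72 = $1,389 and 100,000/120 = $833 per extra engaged patient.

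**An assumed range for T.** Suppose $500 to $2,000 per provider, purely for scale. Then T runs from 100 × $500 = $50,000 to 120 × $2,000 = $240,000. The shortfall runs from 50,000/120 = $417 to 240,000/72 = $3,333.

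**Spreading the cost.** If m patients benefit, the shortfall is T/(m × ΔE). With m = 960, for example, and the same ΔE, the figures per $100,000 halve to 100,000/240 = $417 and 100,000/144 = $694.

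**Effect on the acceptability curves.** At threshold λ the curve shows the probability that λΔE − ΔC exceeds zero. Omitting T lowers ΔC by T/n ($100,000/480 = $208 per patient) at every λ. If T/n is treated as a fixed amount, the plotted probability can only stay the same or rise.

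**Does another part of the plan restore the cost?** The listed examples of counted costs include no training item. The promised sensitivity analyses concern estimates that are imprecise or poorly informed. They do not commit to adding back an excluded category.

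**The case against.** The strongest defence is that the analysis concerns routine delivery of ED-initiated buprenorphine once start-up is over. The cost examples fit that reading, and the exclusion is open and reasoned. As a secondary analysis it is coherent. It does not fit a ratio defined by IF versus baseline, or curves said to compare implementation strategies. If it is what was meant, the label is wrong and the perspective is unstated.

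A second defence is that training here means training of research staff. The sentence does not say so. It names training alongside research as a separate item, and protocol 13.0 uses the word for both research associates and providers.

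Several stronger readings are tempting but unsupported:

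- **That the whole cost of delivering IF is excluded.** The rule names only training and research. Facilitators, champions, feedback and marketing are separate items in Table 1. The plan is silent on them, and the list of counted costs is open-ended.
- **That the ratio is wrong by a known dollar amount.** No training cost is documented. Loading a fixed cost onto 480 enrolled patients gives an upper-end figure, because trained providers also treat unenrolled and later patients.
- **That the ICER is understated whatever the results.** This needs ΔE > 0. The Revised SAP reports that engagement fell at one site, where a site-level ratio would have no useful meaning.
- **That all the data for a correction are in hand.** Protocol 14.8.1 says "At baseline we will collect information on provider wages and space costs to perform interventions to use in cost analysis", and protocol 11.10 gives as an example process measure the "number and types of educational training sessions attended by staff". Neither shows that facilitator, champion or waiver-course hours were recorded.

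**Conclusion.** The point holds for training. Following the rule removes an incremental cost of IF from ΔC while its effect stays in ΔE. For any positive net training cost, the acceptability curves are tilted in favour of IF. If ΔE > 0, the cost per extra engaged patient is also too low.

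The size is T/72 to T/120 at planning values, or about $833 to $1,389 for each $100,000 omitted. This rests on 480 IF-period patients, the planned engagement gain, and the cost being charged to enrolled patients only. The figure falls if others share the benefit. T itself is unknown.

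This is worth correcting but limited in reach. The cost-effectiveness analysis is exploratory, and no primary or secondary comparison depends on it.

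**What to change.** Amend SAP 7.7, and treat the matching sentence in protocol 12.15 as superseded:

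1. Exclude research-only costs, and state the perspective of the analysis.
2. Add incremental IF training cost to ΔC, net of the grand-rounds session. Use the provider wages under protocol 14.8.1, and the training participation and waiver counts named as process measures in protocol 11.3 and 11.10. Estimate hours that were not recorded and vary them in a sensitivity analysis.
3. State whether facilitator and champion time counts as an intervention cost.
4. Report the ICER and acceptability curves with and without these costs. Label the version without them as the delivery cost of ED-initiated buprenorphine, excluding implementation.
5. Say over which patients the training cost is spread, and show at least one alternative.

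The cost is a change of wording and modest costing work. Enrolment closed in October 2020 (SAP 3.3.6), so unrecorded hours would have to be reconstructed. No new patient data are needed. The ICER becomes less favourable to IF.
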